### 02. Specific Aims

Women Veterans (WVs) continue to represent the fastest growing segment of new users of the VA healthcare system, doubling their numbers in the past decade, with 10% of VA users being women by 2018. Their physical and mental health (MH) needs have proven to be more complex than their male counterparts, including a high rate of military sexual trauma (MST) that places them at greater risk of depression, anxiety and posttraumatic stress disorder (PTSD), while also complicating medical management and requiring gender-sensitive care environments. Most VA providers also have minimal exposure to women, creating deficits in needed knowledge and experience. Historical gaps in VA provision of women's health (WH) care have also resulted in WVs being more likely to be referred to community providers, adding to their care fragmentation and contributing to persistent gender disparities in VA quality of care and patient experience.

These trends have required multiple initiatives to change VA culture to be more gender-sensitive, set minimum standards for training and proficiency of designated WH providers, and delineate features of acceptable primary care clinic models that integrate gender-specific and MH services in "one-stop shopping" approaches. VA Women's Health Services (WHS) has led these efforts and set forth an updated VA policy on "Health Care Services for Women Veterans" (VHA Handbook 1330.01, May 2010), which seeks to systematically improve WVs' access to comprehensive healthcare services delivered by proficient providers and staff in environments that ensure WVs' safety, security and dignity. In the same year, WHS launched an annual Women's Assessment Tool for Comprehensive Health (WATCH) to evaluate Handbook implementation, and an external evaluation comprised of site visits to over 84% of VA medical centers (VAMCs). Together, these evaluation activities have documented substantial progress and informed strategic planning and decision-making in terms of policies and resources needed to improve VA WH programs nationwide.

However, the evaluations also found that traditional top-down policy implementation—even when leveraged by evaluation feedback and multilevel WH champions at the clinic, VAMC, VISN and national levels—has not been uniformly successful in achieving the tenets of VA policy on comprehensive WH care. WHS has begun to identify consistently low-performing VA facilities that would benefit from more focused organizational interventions. Based on previous success using evidence-based quality improvement (EBQI) as an implementation strategy that fosters local engagement and multilevel stakeholder activation around improvement goals, WHS will rollout EBQI in low-performing VA facilities starting in FY17. WHS's EBQI approach, which will be implemented by an already-approved contractor, builds directly on the bundle of activities being tested in one of the five WH CREATE studies (CRE 12-026), which itself was based on EBQI efforts in multiple VA randomized trials. These activities include local site visits designed to achieve consensus on QI targets, multilevel stakeholder engagement, external practice facilitation, local EBQI team training, and formative feedback, for which technical specifications have already been developed.

We have worked closely with WHS to design a convergent parallel mixed methods evaluation in the context of a dynamic waitlisted design to evaluate the effectiveness of EBQI implementation on achievement of comprehensive WH care in low-performing VA facilities. Building on our substantial prior experience implementing and evaluating EBQI in VA, we propose the following specific aims:

**Aim #1**: To evaluate barriers and facilitators to achieving delivery of comprehensive women's health care in the identified low-performing VA facilities;

Aim #2: To evaluate the effectiveness of EBQI in supporting low-performing VA facilities achieve improved:

- a. Organizational features (e.g., level of comprehensive services available, care coordination arrangements, PACT features implemented, environment of care improvements);
- b. Provider/staff attitudes (e.g., improved gender awareness, WH knowledge and practice);
- c. Quality of care and patient experience among WV patients; and,

**Aim #3**: To evaluate contextual factors, local implementation processes, and organizational changes in the participating facilities over time.

Evaluation results will inform strategies for optimizing future policy deployment and multilevel engagement strategies with the field, while also informing best practice diffusion. The focus on low-performing VAs will offer new insights, as these less-studied facilities may require uniquely concentrated and/or tailored efforts.

### 02a. RESEARCH PLAN (EVALUATION PLAN)

# A. BACKGROUND

**A1. Gaps in Comprehensive Care for WVs**. Historically plagued by gaps in safety and privacy for women in VA facilities originally designed for men, with a workforce with little to no exposure to female patients, the VA has faced significant challenges in meeting WVs' complex care needs. Ensuring access to gender-specific care and a full complement of reproductive and gynecologic health services has also contributed to higher rates of community referrals among WVs, further fragmenting their care. These and other challenges have led to persistent gender disparities in VA care quality and patient experience.

Over a decade ago VA stood up a handful of comprehensive WH centers in response to Government Accounting Office findings of gaps in WVs' care, and subsequent legislation. WH clinics grew 8-fold over the next decade. However, only a fraction delivered comprehensive services like the original model programs, many focusing on gender-specific exams to help increase VA breast and cervical cancer screening rates. Nonetheless, adoption of WH clinic models was associated with higher preventive practices and higher WV ratings of access, continuity, coordination, and satisfaction.

**A2. VA Policy Aimed to Respond to Gaps in Care**. In 2010, VA WHS launched a 5-year strategic plan to redesign the nation's healthcare delivery system for WVs, with guidance on required use of designated WH providers (DWHPs) for primary care (PC), acceptable PC model features with integrated MH and gender-specific care, and a set of required comprehensive services (VHA Handbook 1330.01, May 2010). Added were explicit expectations that all VA care environments must afford WVs a sense of safety/security, supply same-gender providers (if preferred), and address gender-sensitivity across the spectrum of VA services.

**A3. Evaluation of Comprehensive Care Policy Implementation.** WHS contracted with a private sector firm from 2010-15 to gauge progress towards full Handbook implementation through site visits that included interviews with approximately 20 individuals/groups, case discussions, facility tours, and a review of program-related documents. Each VAMC's capabilities were then scored (from "needs development" to "highly developed") through focused team consensus sessions across 33 Handbook-related domains. Site visits concluded with closing conferences with leadership, followed by Site Visit Summary Reports and Score Cards for each site. WHS received dashboard updates for distinctively high- and low-end performers on program components and capabilities by facility and VISN.

Major problematic findings included gaps in organizational structure (e.g., WV Program Managers being assigned collateral duties, precluding focus on policy-mandated roles and responsibilities), inadequate oversight or planning, major gaps in privacy/security in exam rooms, limited cross-coverage for key WH roles, environments not welcoming to women, gaps in comprehensive care in community-based outpatient clinics, staffing insufficiency (including below-standard staffing ratios, high panel sizes, limited WH experience/training), and limited efforts to improve cultural competency and gender sensitivity of staff.

**A4. WHS/HSR&D Collaboration to Accelerate Comprehensive Care Implementation.** WHS has long been funding the applicant HSR&D investigators and their colleagues to conduct evaluation activities of WVs' health conditions and use (e.g., WV Sourcebooks), needs and experiences (e.g., National Survey of WVs), and evaluations of VA WH programs (e.g., telegynecology). In2012, WHS funded the applicant team to conduct a national expert panel to define gender-sensitive comprehensive care to improve its measurement. WHS then worked with us as primary partner for the WH CREATE, a partnered collaborative research initiative funded by VA HSR&D to use research to further accelerate implementation of comprehensive care for WVs. All five CREATE studies launched in early 2013, including a national organizational survey of comprehensive care arrangements based on the panel results, and a 12-VAMC trial of an EBQI approach to tailoring Patient Aligned Care Teams (PACT) to the needs of WVs. The WH CREATE is an integral initiative supported by the VA WH Research Network (WHRN), which the Blueprint for Excellence cited as central to accelerating innovations in VA WH care (Transformational Strategy 7.2.g).

**A5. WHS Main Evaluation Goals**. WHS seeks a partnered evaluation of their rollout of EBQI as a new strategy for improving quality of WH care in consistently low-performing VA facilities. Building on early evidence of EBQI's promise in activating local teams and leadership around WH PACT improvements, WHS asked for technical specifications to enable contracting for EBQI. They then asked us to adapt our WH PACT EBQI evaluation methods—specifically, key stakeholder (KS) interviews, provider/staff surveys, and

analysis of secondary data—to determine the ways in which EBQI may help low-performing VAs improve quality of care. In our WH PACT study, these methods and measures have revealed new information on WVs' needs and experiences, elucidated implementation barriers, and helped identify actionable provider/staff attitudes and knowledge gaps.

**A6. Conceptual Framework for Evaluation**. We have adapted our conceptual framework from the WH PACT trial for the proposed evaluation (*Figure* below). In this evaluation, a contractor working under technical specifications for EBQI (*far left column*) will: 1) convene facility-level stakeholder meetings; 2) facilitate local facility-level QI team design meetings; and 3) provide external practice facilitation through within- and across-facility QI collaboration calls, QI data feedback and QI training/education. Initial results of EBQI implementation will include local QI actions (e.g., strategic project activities, structured QI proposals, and multilevel review in advance of conduct), and improved provider and staff QI orientation, WH

knowledge/awareness, and gender awareness (*middle column, top*). These actions will occur in the context of each VAMC's leadership support, local resources, pre-EBQI WH care model and staffing, pre-EBQI provider and staff QI and WH experience, awareness and attitudes, as well as area characteristics (e.g., urban/rural location) (*middle column, bottom*).

Our evaluation activities map directly to this conceptual framework using a formative evaluation framework designed to identify the potential and actual influences on progress and effectiveness of implementation efforts. For example, we will evaluate the EBQI contractor's implementation of EBQI methods (*first column*) under **Aim #1** as a developmental evaluation stage (e.g., degree of less-than-best practice, determinants of current practice, barriers/facilitators and feasibility/perceived utility). Under **Aim #2**, we will conduct a progress-focused evaluation of EBQI effectiveness on achievement of comprehensive care (right column), monitoring impacts and indicators of progress toward goals, with feedback to WHS and the EBQI contractor. **Aim #3** will cover two types of evaluation. First, we will conduct an implementation-focused evaluation (also known as process evaluation) to examine discrepancies between EBQI implementation plans and how the EBQI contractor actually operationalizes them, helps identify influences we might otherwise have not considered, will enable us to describe experiences of those undergoing EBQI implementation, and will consider the context in which facilities participate (12-month key stakeholder interviews [**§B4a**] will be especially important). Second, we will use results from all of the other evaluation stages to conduct an interpretive evaluation (24-month key stakeholder interviews will be key here).

# **B. METHODS (EVALUATION PLAN)**

# **B1. Evaluation Plan Overview**

We will conduct a convergent parallel mixed methods evaluation in the context of a dynamic waitlisted design to evaluate the effectiveness of EBQI implementation on achievement of comprehensive WH care in low-performing VA facilities. For **Aim #1 (developmental evaluation)**, we will rely on key stakeholder interviews (§B4a), organizational surveys (§B4b), and administrative data (§B4d) at baseline and ahead of each phased implementation launch of another wave of VA facilities. For **Aim #2 (progress-focused evaluation)**, we will use organizational surveys (§B4b), provider/staff surveys (§B4c), and secondary data on WVs' quality of care and patient experience (§B4d). For **Aim #3 (implementation-focused & interpretive evaluations)**, we will re-interview Aim #1 key stakeholders, with a focus on implementation processes and organizational changes at 12 and 24 months (§B4a).

# **B2. Evaluation Design**

The choice of a dynamic waitlisted design is based on WHS's plans for staged EBQI implementation at no more than eight VA facilities per year for the next three years for a total of 24 facilities. This randomized "roll-out" implementation design has very good statistical properties, including higher power than traditional

wait-listed designs and less vulnerability to external, uncontrolled factors. EBQI implementation will commence in Year 1 (FY17) in eight randomly selected facilities (Group 1), with the remaining 16 facilities serving as waitlisted controls. In FY18, eight of these waitlisted controls will be randomly selected for EBQI implementation (Group 2), leaving the remaining eight as waitlisted controls in FY18, which will begin EBQI implementation in Year 3 (Group 3).

## **B3. Study Population and Sampling Strategy**

# Figure 1. Staged EBQI Implementation

In the first 30 days of FY17, with input from WHS and the evaluation team, the EBQI contractor will analyze prior site visit assessment data (Booz-Allen-[name] FY16 report), local VA facility self-assessment data (WATCH) (**Appendix 2**), and selected performance measures to identify the lowest-performing VAs (bottom 25-30%) of previously assessed sites nationwide and by VISN. In FY17Q1, WHS will make the final site selection decision (n=24 VA facilities) that will be the focus of EBQI implementation and evaluation.

## **B4. Data Sources, Measures and Data Collection Approaches**

The proposed data sources are a direct result of WHS input on and preferences for evaluation design, and their experience with these sources under the WH CREATE and previous evaluations we have conducted with and for WHS. In particular, the evaluation will substantively benefit from use of existing instruments from the WH CREATE, including the national VA organizational survey modules noted above (CRE 12-038) (including national secondary data on quality metrics and patient experience) and the WH PACT trial (CRE 12-026) (including KS interview guides and provider/staff surveys). Below we describe each evaluation data source's sampling plans, measures, and data collection procedures.

B4a. Key Stakeholders (KS). Semi-structured gualitative interviews will be conducted at baseline for all sites (Aim #1), as well as immediately prior to the EBQI launch of Groups 2 and 3. Interviews will be conducted at all sites at 12 months post-EBQI launch; in Group 1, interviews will also be conducted at 24 months. Sampling Plan: For Aim #1, we will work with the EBQI contractor to identify facility-level KS (e.g., quadrad member, PC director, WH medical director, WVPM, QI/system redesign lead; n~6/facility) and VISN-level KS (e.g., VISN director, VISN Lead WVPM, VISN system redesign lead; n~4/VISN). We will also interview WHS leaders and EBQI contractor personnel to evaluate leadership and implementation processes. We will adapt KS selection based on the QI targets established at initial EBQI site visits (e.g., add a MH director if the QI project targets MH). For Aim #3, we will seek to re-interview the same KS as in Aim #1, but will pursue replacement personnel in the event of turnover and/or position changes over time. Measures: The Aim #1 baseline interview guide (Appendix 3) includes guestions about the structure and delivery of usual care for WVs, barriers and facilitators to achieving delivery of comprehensive WH care, what (if any) improvements are underway in WH and/or for WVs, familiarity with performance metrics, access to metrics by gender, experience with QI, local culture, perceptions of the care environment, and engagement. The Aim #3 12- and 24-month interviews will assess any changes in care for WVs (staffing, structure, etc.), details of completed/in progress QI projects, perspectives on critical components of EBQI, and anticipated sustainability of local improvements and QI methods. Data Collection: Under the supervision of [name] (Co-PI), KS interviews will be conducted by telephone, recorded and professionally transcribed. Transcripts will be reviewed and edited for accuracy.

**B4b. Organizational Surveys.** We will use key informant organizational surveys at baseline, 12- and 24months among the 24 participating VA facilities, in addition to annual administered WATCH surveys from WHS (Aim #2a). For Year 1 (FY17), we will rely on national organizational survey modules that will be fielded in Quarter 1 (Q1) as part of a WH CREATE study ([name] & [name], Co-PIs, CRE 12-038) (**Appendix 4**). For Years 2 and 3 (FY18-19), we will re-administer the same surveys, adapting selected domains in relation to EBQI targets of participating VAs. Sampling Plan: All 24 participating VA facilities, including modules for PC directors, WH medical directors, MH directors and WV Program Managers (WVPMs). We will use the tailored design method to identify named respondents for each module. Additional key informants (e.g., chief of medicine) may be considered in subsequent waves if local EBQI targets warrant it. *Measures*: We will include measures of *leadership support*, *local resources* (e.g., sufficiency of time, personnel, equipment), practice structure (e.g., WH care model, staff mix, referral arrangements), *service availability*, *care coordination arrangements* (within and outside VA), *ability to engage in QI* (e.g., barriers to QI, data access by gender), *gender-sensitivity of environment* (e.g., privacy), *local challenges* (e.g., provider shortages, hiring difficulties, practice chaos), *facility type* (e.g., size, academic affiliation, urban/rural), and *EBQI activities*. *Data Collection*: We will field surveys through REDCap, a VA-approved web survey vendor.

**B4c. VA Providers/Staff Surveys**. We will use web-based provider/staff surveys at baseline, 12- and 24months. Sampling Plan: We will obtain lists of local providers and staff using the same protocol used previously to identify PC and WH providers/staff, drawing a census from Primary Care Management Module (PCMM) data for each participating facility (including PACT teamlets and larger PACT teams [e.g., pharmacists, social workers]). In the 12-VA WH PACT trial, this approach yielded 775 providers and staff across urban and rural VAMCs; we anticipate identifying roughly twice as many personnel in the 24-facility evaluation. If other work units are prioritized by WHS (e.g., MH provider/staff), we will adapt the same approach but using VA PAID and other administrative sources, with local sample validation. Measures: We will include measures of *EBQI exposure/participation* (e.g., awareness, hours spent, local buy-in), *QI orientation/culture* (e.g., perceived cooperation among managers/providers/staff, communication effectiveness, culture fostering flexibility, participative decision-making), gender sensitivity (e.g., awareness, knowledge, attitudes, self-assessment of WH proficiency), practice context (e.g., leadership norms, organizational readiness to change, job satisfaction, burnout), and provider/staff *characteristics* (e.g., age, gender, race, ethnicity, staff type, clinician type, DWHP, proportion of WVs in panel/clinic, board certification, years in VA) (**Appendix 5**). Data Collection: Consistent with prior procedures, we will send pre-notification emails, then email invites with an embedded survey weblink, Q&A, and endorsement letters from WHS and local leadership. Email reminders will include a hardcopy option.

B4d. VA Administrative Data. We will pull secondary data on WV-specific VA quality of care and patient experience, in addition to utilization patterns and other administrative data. Sampling Plan: Each VA data source (e.g., chart-based External Peer Review Program [EPRP] quality metrics; Survey of Healthcare Experiences for Patients [SHEPs]) has its own sampling plan, limiting our latitude and also statistical power as WVs are not currently sufficiently over-sampled at the facility-level. For *quality metrics*, we will address this by applying existing programming code from WHS for generating EPRP-like measures on the population of WVs seen in each participating facility from the Corporate Data Warehouse (CDW). We will also obtain comparable CDW-derived metrics from the National PACT Evaluation team for PACT Compasslike measures (e.g., average wait time, non-face-to-face visit use). For survey metrics, we will explore aggregated SHEPs data by Group (1/2/3) and over time, and examine contextual differences in the sample of WVs seen in the 24 participating facilities compared to VAs of similar facility complexity. Because the sample of low-performing facilities has not yet been identified, we cannot as yet estimate available sample sizes. Measures: CDW-derived metrics will include process measures of quality for diabetes and cardiovascular disease (e.g., lipid screening) care and intermediate outcome measures (e.g., glycemic and lipid control). SHEPs metrics will include access, continuity, coordination, courtesy and overall satisfaction with VA care. PACT Compass-like measures include additional measures of access (e.g., average wait time, % enrolled in PC-MH integration [PC-MHI]), continuity (% of visits with PACT team providers), coordination of care (e.g., emergency room use) and non-face-to-face access (e.g., secure messaging; telephone visits; group visits). We will include utilization measures on PC, WH, MH, specialty care visit rates, in addition to hospital and emergency room use each year. We will also include area measures (e.g., urban/rural location, academic affiliation, facility complexity score). Data Abstraction: We will pull data from CDW through VINCI and/or obtain data elements directly from WHS for use in evaluation.

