In Q2, we will continue with KS interviews, including WHS and EBQI contractor interviews and extending the KS sample to accommodate EBQI targets in Group 1 (e.g., MH leads). We will update the provider/staff survey sample lists, and work with site-level evaluation contacts on sample validation and updated cover letters as needed (i.e., to accommodate leadership changes). By the end of Q2, we will deliver KS summaries and organizational survey findings. We will launch the second wave provider/staff surveys in Q2. We will also pull a second year of administrative data, and provide WHS with a summary report on changes.

In Q3, we will finish the provider/staff survey wave, clean the data and deliver an initial summary report. KS analysis will continue. KS contrasts between Year 1-2 will be reported, in addition to early findings regarding Aim #3 contextual factors and implementation processes based on both waves. Additional organizational analyses with linked administrative data for Aim #2 will also be reported (e.g., variations in resource sufficiency by large and small low-performers).

In Q4, organizational changes based on KS interviews and organizational surveys between Years 1 and 2 overall and by EBQI vs. waitlisted controls will be reported to WHS. We will deliver a second annual report for WHS, summarizing findings across evaluation data sources for FY18, with notable FY17 comparisons.

**FY19**: In Q1, the EBQI contractor will launch EBQI in the remaining low-performing VA facilities. We will again update the KS sample as needed, and launch the third and final wave of KS interviews and again

extend the KS sample to accommodate EBQI targets in Groups 1 and 2 that will have had two and one year of EBQI, respectively. We will start with the baseline KS interviews for Group 3, followed by the KS followup interviews for Groups 1 and 2, which may carry over into Q2. We will again repeat OASC and Union review, and launch the third and final organizational survey wave.

In Q2, we will complete the KS interviews, and initiate rapid KS analysis. We will update the provider/staff sample for the third wave, repeat sample validation steps with participating sites, and prepare endorsement letters once again, and launch the survey by the end of Q2. By the end of Q2, we will also provide WHS with the third wave of KS summaries and an organizational survey summary in the quarterly report.

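### The calendar schedules no post-launch interview for Group 3, so at most 16 of 24 sites can have the promised 12-month interview; the provider/staff survey waves need a time origin and a check on Group 1's baseline

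*Combined protocol and SAP*

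**What the plan says.** **Interviews.** B4a commits to key stakeholder interviews after launch without exception by group: "Interviews will be conducted at all sites at 12 months post-EBQI launch". Group 1 is also to be interviewed at 24 months. In A6 the implementation-focused evaluation "will consider the context in which facilities participate (12-month key stakeholder interviews", and the same bracket singles those interviews out as especially important. B1 bases Aim 3 on re-interviews at 12 and 24 months.

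The calendar in D2 reads differently. In FY19 Q1 "the EBQI contractor will launch EBQI in the remaining low-performing VA facilities", which is Group 3. In the same quarter the team will "launch the third and final wave of KS interviews". The order of work is: "We will start with the baseline KS interviews for Group 3, followed by the KS followup interviews for Groups 1 and 2". In FY19 Q2, "we will complete the KS interviews, and initiate rapid KS analysis". The entries for FY19 Q3 and Q4 list coding and reporting but no further interviews.

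**Surveys.** B4c says: "We will use web-based provider/staff surveys at baseline, 12- and 24months". It does not say from when the months are counted. B4b uses almost the same words for the organizational surveys: "We will use key informant organizational surveys at baseline, 12- and 24months among the 24 participating VA facilities". In D2 the organizational surveys are fielded in Q1 of FY17, FY18 and FY19. The provider/staff surveys open by the end of FY17 Q3, in FY18 Q2, and by the end of FY19 Q2. The first provider/staff wave has follow-up into FY17 Q4 and feeds the Aim 2 baseline report.

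**The concern.** B4a and D2 cannot both hold for Group 3. If the calendar stands, one third of the sites contribute no interview evidence from after launch, while the text tells the reader that all sites do. Aim 3 conclusions on process and context would then appear to rest on wider coverage than they have.

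The provider/staff survey is the stated source for Aim 2b (attitudes, gender awareness, knowledge and practice). Its time points have no origin, and its first wave comes two quarters after the Group 1 sites are allocated. If Group 1 had launched by then and the wave were still used as its pre-launch value, any effect already present would be subtracted from Group 1's change. B6a discloses the employee-survey and Union reviews that delay this wave, but not that consequence.

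**Working it through.** No sample-size or power figure is involved; this is calendar arithmetic. Months are counted from the start of FY17: FY17 Q1 = 0-3, Q2 = 3-6, Q3 = 6-9, Q4 = 9-12; FY18 Q1 = 12-15, Q2 = 15-18; FY19 Q1 = 24-27, Q2 = 27-30; FY19 ends at 36.

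**1. Group 3 interviews** (D2, FY19 entries)
- Launch falls in months 24-27, and interviewing is completed in months 27-30.
- Longest possible time from launch to the last interview: 30 - 24 = 6 months.
- Group 3's 12-month mark: 24 + 12 = 36 to 27 + 12 = 39, at or after the end of the calendar.
- Sites that can have a 12-month interview: at most 24 - 8 = 16. The shortfall is 8/24 = 33%.

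**2. Spacing of survey waves, by opening quarter.** Nominal spacing is the difference between quarter starts. The range runs from (later quarter's start - earlier quarter's end) to (later quarter's end - earlier quarter's start).

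| Interval | Nominal (months) | Range (months) |
|---|---|---|
| Provider/staff wave 1 to 2 | 15 - 6 = 9 | 15 - 9 = 6 to 18 - 6 = 12 |
| Provider/staff wave 1 to 3 | 27 - 6 = 21 | 27 - 9 = 18 to 30 - 6 = 24 |
| Provider/staff wave 2 to 3 | 27 - 15 = 12 | 27 - 18 = 9 to 30 - 15 = 15 |
| Organizational wave 1 to 2 | 12 - 0 = 12 | 12 - 3 = 9 to 15 - 0 = 15 |
| Organizational wave 1 to 3 | 24 - 0 = 24 | 24 - 3 = 21 to 27 - 0 = 27 |

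The organizational surveys reproduce 12 and 24 months. The provider/staff waves are nominally one quarter (3 months) short of each, because the first wave is late; the second interval is itself about 12 months. These are opening dates. Wave 1 fielding runs into FY17 Q4 and wave 2 into FY18 Q3, so individual responses are spread more widely.

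**3. Is wave 1 pre-launch?**
- Group 2 is allocated in FY18 Q1 (month 12 or later) and Group 3 launches in FY19 Q1. Wave 1 follow-up ends in FY17 Q4 (by month 12). Wave 1 is therefore pre-launch for 8 + 8 = 16 sites.
- Group 1 is allocated in FY17 Q1. B2 gives its launch only as FY17, so the quarter is an assumption. For wave 1 opening in FY17 Q3 (months 6-9), time since launch is:
  - launch in Q1: 6 - 3 = 3 to 9 - 0 = 9 months
  - launch in Q2: 6 - 6 = 0 to 9 - 3 = 6 months
  - launch in Q3: 6 - 9 = -3 to 9 - 6 = 3 months
  - launch in Q4: 6 - 12 = -6 to 9 - 9 = 0 months
- D2 credits Group 1 with two years of EBQI at FY19 Q1. A Q1 launch gives 24 - 0 = 24 months nominally and a Q2 launch 24 - 3 = 21 (24 at the outer edge). Launches in Q3 and Q4 give 18 and 15. That wording therefore points to the first half of FY17, before wave 1 opens.

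**The case against.** On the interviews there is no good answer. Reading 12 months as nominal does not help, because D2 lists no post-launch interview of any duration for Group 3.

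On the surveys the objections carry real weight.
- D2 gives the end of FY17 Q3 as a deadline. Spacings of 12 and 24 months are reachable at the extreme edge of the ranges, so a reader should not infer that they are impossible.
- A reader might infer that Groups 2 and 3 are owed surveys 12 and 24 months after their own launches. The documents do not support this. B4a ties its interviews to launch; B4c does not, and B4b uses like wording for common calendar waves. Common waves in a staged roll-out cannot give every group the same launch-relative points, so their absence only restates the design.
- A reader might infer that Group 1's baseline is known to be contaminated. It is not. The launch quarter is absent from the visible text, and Figure 1, on staged implementation, is not shown and may give it.
- A reader might infer that the planned model is biased. B5b specifies no change-from-baseline analysis. It regresses on EBQI exposure, meaning level of implementation, and on time, with random site intercepts. That model can already treat an early Group 1 wave as exposed. B4b, B4c and D2 also plan to record EBQI activities, participation and procedures.

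What stands is that no section says that launch dates are recorded or how exposure is set for each site and wave, while the wave carries the label of baseline.

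**Conclusion.** The interview point is a direct contradiction and wrong as written: at most 16 of 24 sites can have a 12-month interview, and the calendar gives the other 8 no post-launch interview at all. This rests only on dates in D2 and on groups of eight; B6b says up to eight per year, so the counts could shift.

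The survey points are clarifications. The provider/staff waves have no time origin and, as calendar waves, fall about one quarter short of 12 and 24 months. Their first wave is surely pre-launch for Groups 2 and 3 and probably post-launch for Group 1, on the assumption that the two-year credit in D2 is roughly literal. Any resulting loss of effect in Group 1 is conditional on that wave being used as its pre-launch value. Its size depends on the launch date and on how fast effects appear, so no figure can be given.

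Nothing here faults the organizational survey baseline, fielded in FY17 Q1, or the lack of unexposed sites at the last wave, which is normal for a roll-out.

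**What to change.** 1. **B4a and D2.** Reconcile them: state that the 12-month interviews cover Groups 1 and 2 (16 sites), and limit post-launch Aim 3 conclusions to those sites. Label any later Group 3 interview by its actual time since launch.
2. **B4c.** State the time origin and the actual calendar spacing of the three waves.
3. **B5b.** Record each site's launch date and each survey date, and code EBQI exposure at each site and wave from them. A Group 1 site already launched at wave 1 then counts as exposed, and that wave is not used as its pre-launch baseline. Fix the form of the exposure term before any outcome analysis.

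The cost is rewording and date recording, with no new data collection, and some loss of precision if exposure is split by duration. A late Group 3 interview is optional and not free. In FY19 Q4 (months 33-36) it would fall 33 - 27 = 6 to 36 - 24 = 12 months after launch. At about 6 facility-level interviews per site (B4a) and 30 minutes each (B6c), it would need 8 x 6 = 48 interviews, or 48 x 0.5 = 24 interview hours, in the quarter when the Aim 3 results are due.
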